## 4.5 Randomization

Individuals who complete baseline testing (described below, section 6.2) will be randomized 1:1 to banding or metformin using permuted block randomization stratified by gender, BMI (30-35 vs. 35-40 kg/m^2) and diabetes (no vs. yes when IDE approved) to minimize skewing. Individuals assigned to metformin will be given study medications and instructions at the end of the second baseline visit, to begin treatment the following day. Individuals assigned to gastric banding will be scheduled for pre-operative screening with the goal of having them undergo operation within two weeks.

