## 9.1 Primary Outcomes and Analyses

Two primary outcomes, each measuring ß-cell function, will be used to compare the two intervention groups at the end of the treatment period. ANCOVA will be the primary approach used for the analysis. We will employ White's robust (information sandwich) estimate of the covariance matrix of the model coefficients as the basis for inferences. This approach preserves power and protects the type 1 error probability when the homoscedastic normal errors assumptions are violated. All analyses will be adjusted for the baseline value of each endpoint. Both primary outcomes will be analyzed separately with a total type I error probability of 0.05 for each, i.e. without an adjustment for 2 separate outcomes.

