# 9.2 Secondary Outcomes and Analyses

Comparisons of the primary study outcomes will be made for those with vs. without diabetes at study entry, BMI <35 kg/m2 vs. ≥35 kg/m2 at study entry, by race/ethnicity and sex, by baseline HbA1c and β-cell function, and by categorical groups of various biomarkers.

Analysis of covariance will be used to compare the metformin and gastric band groups for additional continuous variables of interest at both the 12-month and 24-month time points relative to the start of the interventions. As for the primary outcomes, all analyses will be adjusted for the baseline value of each endpoint.

An important secondary analysis of this study is to determine whether ß- and  $\alpha$ -cell function from OGTT and fasting samples are sufficiently well correlated with more robust assessments of ß- and  $\alpha$ -cell function obtained from the hyperglycemic clamp to validate their use in large clinical trials. For these analyses, Pearson and non-parametric Spearman correlations of simple versus sophisticated measures of ß- and  $\alpha$ -cell function will be computed.

To examine biomarker associations with glucose metabolism, Pearson and non-parametric Spearman correlations of each biomarker with ß- and  $\alpha$ - cell function, insulin sensitivity and glucose tolerance measures will be determined. In addition, multiple linear regression models

will be developed to predict measures of glucose metabolism with the most informative biomarker sets.

Other planned secondary analyses will examine relationships between exposure variables such as body weight and fat, insulin resistance; circulating adipokines and fat metabolites, and glucose levels and primary and secondary β-cell outcomes within and across treatment groups.

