# 9.3 Sample Size/Power Calculations

We calculated sample size and power based on practical and statistical considerations. Practically, we can perform surgery on 44 subjects within the time frame and budget of the NIH U01 grant and associated support from Allergan. Allowing loss to follow-up rate of 10% per year, this will give us ~35 subjects per group to complete 24-months follow-up. Statistically, with 35 subjects/group, by using two-group t-test we can detect a minimum effect size of 0.68 in difference between the two intervention groups with type I error of 0.05, 2-sided t-test, and 80% power. Adjustment for baseline value using analysis of covariance will give us 89% power to detect the minimal effect size of 0.68, or give us 80% power to detect a minimal effect size of 0.59 when the baseline and follow-up are correlated with a correlation coefficient of 0.5.

Feasibility of observing this effect size is supported by data from diabetes prevention studies using weight loss, TZDs or metformin, as follows:

- The diabetes risk reduction associated with a mean 12 lb. weight loss in the DPP was 58%, similar to the 55% risk reduction in TRIPOD, where we have direct measures of beta cell function. Those measures revealed an effect size of 0.33 for  $\beta$ -cell compensation between placebo and troglitazone at two years.
- Given the similarity of diabetes risk reduction between TRIPOD and the DPP and assuming mitigation of adverse effects of obesity as a primary mechanism for diabetes prevention in both studies, we estimate an effect size for  $\beta$ -cell compensation of 0.33 for weight loss of ~12 lbs. vs. placebo.
- Gastric band patients at USC had an average weight loss of 35 lbs. at 24-months (Figure 1, above), nearly three times the average weight loss seen over the course of the DPP. Thus, we may see an effect size of 3 x 0.33 = 0.99 for  $\beta$ -cell function in gastric banding compared to no treatment.
- Diabetes risk reduction with metformin in the DPP was 31%, approximately 53% of the reduction seen with lifestyle induced weight loss. If all of the protection were due to preservation of β-cell compensation, this would represent and effect size of ~0.18 vs. placebo.

The differential in projected effect sizes between band-induced weight loss (~0.99) and metformin (~0.18) is ~0.80, well above the 0.68 or the 0.59 minimal effect sizes that we have the power to detect with our study design.

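### Section 9.1 names White's sandwich without a small-sample correction or reference distribution; read as HC0, it runs slightly above 5% at 35 per arm and further above in small subgroups

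*Combined protocol and SAP*

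**What the plan says.** Section 9.1 makes ANCOVA the main method for both co-primary endpoints and fixes the variance: "We will employ White's robust (information sandwich) estimate of the covariance matrix of the model coefficients as the basis for inferences". The justification follows at once: "This approach preserves power and protects the type 1 error probability when the homoscedastic normal errors assumptions are violated". No sample size is attached to that claim, no finite-sample variant is named, and nothing says whether the statistic is referred to a normal or a t distribution.

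The only covariate named is the baseline value: "All analyses will be adjusted for the baseline value of each endpoint". On error control: "Both primary outcomes will be analyzed separately with a total type I error probability of 0.05 for each", with no adjustment for having two endpoints.

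Section 9.3 gives the size: "Allowing loss to follow-up rate of 10% per year, this will give us ~35 subjects per group to complete 24-months follow-up". Its power figures are computed "with type I error of 0.05, 2-sided t-test, and 80% power", and then for ANCOVA with a baseline correlation of 0.5. Section 4.5 plans equal arms: participants "will be randomized 1:1 to banding or metformin using permuted block randomization".

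Section 9.2 repeats the primary comparisons by diabetes status, BMI, race/ethnicity, sex, baseline HbA1c, baseline β-cell function and biomarker categories. It gives no subgroup sizes and does not say whether these are separate fits or interaction tests. For the additional continuous outcomes it carries over the covariate ("As for the primary outcomes, all analyses will be adjusted for the baseline value of each endpoint") but does not mention the sandwich.

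**The concern.** White's estimator in its basic form (HC0) plugs in squared raw residuals. After p coefficients have been fitted, residuals are on average smaller than the errors they stand for, so the variance of the treatment effect is underestimated. Normal critical values add to this by ignoring the uncertainty in the estimated standard error. Both effects vanish in large samples, but 70 patients is not large, and a subgroup is smaller still.

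Two things are at stake. First, since the two co-primary tests are not adjusted for each other, the per-test 5% is the only type I error limit that Section 9.1 sets, and the method as named may not quite meet it. Second, HC0, HC1, HC2 and HC3, each with normal or t critical values, all fit the description and give different p-values. In an open-label trial that choice should be fixed before outcome data are seen.

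**Working it through.** **1. The plan's own figures.** Inputs from Section 9.3: 44 per arm, 10% loss per year, two-sided 5%, r = 0.5.
- Completers: 44 × 0.80 = 35.2, or 44 × 0.81 = 35.6, so about 35 per arm.
- t-test: noncentrality 0.68 × √(35/2) = 2.845, power 80.1% (plan: 80%).
- ANCOVA: the SD is multiplied by √(1 − 0.5²) = 0.866. Power is 89.9% at 0.68 (plan: 89%) and 80.2% at 0.59 (plan: 80%).

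The stated figures reproduce, and none of them uses a sandwich variance.

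**2. Size by hand.** The model has p = 3 coefficients (intercept, arm, baseline). With balanced arms and normal errors, HC0 understates the variance by roughly (n − p)/n. The effective critical value is the nominal one times √((n − p)/n), referred to t on n − p degrees of freedom.
- 35 per arm: √(67/70) = 0.978. Normal: 1.960 × 0.978 = 1.918, two-sided tail 5.9%. t: 1.996 × 0.978 = 1.953, tail 5.5%.
- 17 per arm: √(31/34) = 0.955. Normal: 1.872, tail 7.1%. t: 2.040 × 0.955 = 1.948, tail 6.1%.
- 10 per arm: √(17/20) = 0.922. Normal: 1.807, tail 8.9%. t: 2.110 × 0.922 = 1.945, tail 6.9%.

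**3. Size by simulation.** Baseline-adjusted ANCOVA, r = 0.5, no treatment effect, 60,000 to 400,000 trials per setting. Normal errors:

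| Per arm | HC0, normal | HC0, t | HC2, t |
|---|---|---|---|
| 35 | 5.95% | 5.51% | 5.00% |
| 17 (assumed) | about 7.1% | about 6.1% | about 5.2% |
| 10 (assumed) | about 9.2% | about 7.1% | about 5.4% |

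Separate runs at 17 and 10 per arm differed by up to 0.4 points. At 35 per arm, HC1 with t gave 4.99%, HC3 with t 4.53% and the ordinary ANCOVA t-test 4.97%.

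Other error shapes at 35 per arm were t with 5 df, lognormal, arm SD ratios of 1.5 and 2, and variance rising with a skewed baseline. Across these and the normal case, HC0 gave 5.6 to 6.2% (normal) and 5.2 to 5.7% (t). A heavily skewed case gave 5.1% and 4.7%. Leaving that case aside, HC2 with t held 4.7 to 5.2%, as did the ordinary ANCOVA t-test.

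**4. Interaction instead of separate fits.** For a treatment-by-subgroup test on all 70, HC0 with normal critical values gave 6.3%, 7.1% and 9.0% when the smaller subgroup had 17, 10 and 6 per arm. HC2 with t gave 4.9%, 5.5% and 6.3%.

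**5. Power at 35 per arm, normal errors.**

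| Effect | HC0, normal | HC2, t | HC3, t | Plan |
|---|---|---|---|---|
| 0.59 | 81.8% | 79.6–79.7% | 78.4% | 80% |
| 0.68 | 90.9% | 89.6% | 88.7% | 89% |

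**The case against.** The strongest reply is that the plan never says the estimator is uncorrected. An analyst who takes HC1 with a t reference satisfies the wording and has 4.99% at 35 per arm. This stands. A reader might infer that a defective estimator was chosen, but the documents support only that the variant was left open, with HC0 as the plain reading.

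The sentence in Section 9.1 also concerns violated assumptions, and there a sandwich can help. With 40 versus 30 patients and an SD 1.5 times larger in the smaller arm, HC0 with t gave 5.7% against 6.3% for the ordinary ANCOVA t-test. So the case is not against robust variance as such. With equal arms, as planned, the ordinary test already held its level.

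The subgroup argument is conditional. These are secondary analyses, their sizes are not stated, Section 9.2 does not name the sandwich for them, and the interaction form is generally less affected than a separate fit of the same size.

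Two further inferences should be resisted. One is that the planned 80% power is inflated by HC0; it is not, because Section 9.3 does not use the sandwich. The other is to quote a larger primary error from a model with the stratification factors added. Three binary covariates would raise HC0 at 35 per arm to about 6.6% (normal) or 6.1% (t), but Section 9.1 adjusts only for the baseline value.

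What remains is that the text does not require any correction, while claiming a protection that the plain reading does not fully deliver at this size.

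**Conclusion.** The point holds as a specification gap with a small cost for the primary analysis. At about 35 per arm, the plain reading puts type I error at roughly 5 to 6% with normal critical values and 4.7 to 5.7% with t. A reader might infer that the primary p-values are unreliable; an excess of at most about 1.2 points, and none in the most skewed case, does not support that.

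It matters more in small subgroups if the estimator is carried over: about 7% (normal) or 6% (t) at 17 per arm, and about 9% or 7% at 10. Severity is minor for the primary tests and more material for small subgroups.

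This rests on reading the named estimator as HC0, on r = 0.5 and equal arms (both from the plan), on assumed error shapes, and on assumed subgroup sizes of 10 to 17 per arm.

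**What to change.** In Section 9.1, replace the unqualified reference to White's estimate with a finite-sample-corrected sandwich, for example HC2, and state that tests and confidence intervals use t critical values on the residual degrees of freedom. Qualify the protection claim accordingly. In Section 9.2, say that the same estimator and reference apply to the subgroup ANCOVAs, and whether these are interaction tests or separate fits.

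HC1 does as well as HC2 in the balanced baseline-adjusted fits. In an interaction test with only 6 per arm in the smaller subgroup it does not: HC1 with t gave 7.4%, HC2 6.3% and HC3 4.6%. HC3 is the stricter option.

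The cost is a sentence or two in the plan and one software setting. Power at 0.59 is about 79.7% with HC2 and 78.4% with HC3, against the 80% planned. The correction is not complete in very small cells: HC2 with t still gives about 5.8% at 10 per arm with an SD ratio of 2.

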#### Figure 2.1: Weight Loss in USC Gastric Band Program

Data are from 83 obese individuals with T2D who had follow-up for at least two years. Results were achieved without the intensive approach to band adjustment that we propose for this project.

Data are from 1221 adults (mean age 35 years, mean BMI 29.6 kg/m^2). Insulin sensitivity ( $S_1$ ) was measured with IVGTT-minimal model.

We chose metformin as the comparator for two main reasons. First, we will include people with mild T2D; standards of care dictate that they should receive medical therapy and metformin is the drug most often recommended in this context (23). Metformin is also the only drug that has been recommended for use in diabetes prevention (24). Thus, we will be comparing gastric banding to the current standard of medical monotherapy early in the course of T2D.

We will study people with pre- and mild T2D because we have observed a fairly linear decline in  $\beta$ -cell compensation across this range (9). We are also confident that we can assess insulin sensitivity and secretion across this range. Thus, we will be able to test for arrest or reversal of falling  $\beta$ -cell compensation. Overall, this approach and our expertise  $\beta$ -cell biology and preservation in humans put us in very strong position to make unique and important contributions to the RISE Consortium.

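### The ANCOVA leaves out the randomisation factors (sex, BMI, diabetes); adding them with a small-sample sandwich correction is a cheap refinement worth considering

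*Combined protocol and SAP*

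**What the plan says.** Section 4.5 allocates 1:1 "using permuted block randomization stratified by gender, BMI" (30-35 vs 35-40 kg/m²) and "diabetes (no vs. yes when IDE approved) to minimize skewing". That makes three binary factors and eight strata once all are in force.

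Section 9.1 makes ANCOVA the primary method and names one covariate: "All analyses will be adjusted for the baseline value of each endpoint". Section 9.2 repeats this for the additional continuous outcomes: "As for the primary outcomes, all analyses will be adjusted for the baseline value of each endpoint". The three factors return in section 9 only as subgroup comparisons, for example "Comparisons of the primary study outcomes will be made for those with vs. without diabetes at study entry". The opening of section 9 allows transformations and robust or nonparametric methods but adds no covariates.

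On standard errors, 9.1 says: "We will employ White's robust (information sandwich) estimate of the covariance matrix". It names no small-sample version and no reference distribution.

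**The concern.** Stratified randomisation balances the factors between arms. If they also predict the outcome after adjustment for baseline, a model without them leaves their variance in the error term. The standard error is then too large for the balance actually achieved, so the test is conservative and part of the benefit of stratifying is lost.

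Power is what is at stake, not validity. It matters here because section 9.3 caps the trial at 44 operations, so more patients are not an easy remedy.

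The sandwich estimator is a linked detail. Read literally, White's estimator is the uncorrected HC0, which runs liberal in small samples. In the planned two-parameter adjustment (treatment and baseline) this matters little. It matters more when three covariates are added with about 70 completers.

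**Working it through.** **Inputs from the documents.** 88 participants, 44 per arm (3.1, 9.3); 10% loss per year, about 35 completers per arm; two-sided 0.05; baseline/follow-up correlation 0.5; detectable effects 0.68 (t-test) and 0.59 (ANCOVA); projected effect about 0.80 (all 9.3).

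**Reproducing 9.3.** Completers: 44 × 0.9 × 0.9 = 35.6 per arm. Power is noncentral t with noncentrality (d/σ)·√(35/2).
- t-test, σ = 1, d = 0.68, 68 df: noncentrality 2.84, power 80.1% (stated 80%).
- ANCOVA, σ = √(1 − 0.5²) = 0.866, 67 df: noncentrality 3.28 and power 89.9% at 0.68 (stated 89%); noncentrality 2.85 and power 80.2% at 0.59 (stated 80%); power 96.8% at 0.80.

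The stated figures hold.

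**Adding the factors, by formula.** Three more degrees of freedom are lost (67 − 3 = 64) and σ becomes √(0.75·(1 − s)). Here s is the share of residual variance, after baseline, that the factors explain. The documents do not give s, so I took 0, 5, 10 and 20%. Power at 0.59 is then 80.2%, 82.1%, 84.1% and 88.1%; at 0.80 it is 96.8%, 97.4%, 98.0% and 98.9%.

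**What a share means.** For three balanced factors of equal weight, each with a between-level difference δ, 3·δ²/4 = 0.75·s, so δ = √s. Shares of 5, 10 and 20% need differences of 0.22, 0.32 and 0.45 SD for each factor.

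**Simulation.** The formula assumes exact balance, so I also simulated the randomisation. Assumptions: N = 88, eight strata, each factor at 50%, blocks of 4, 20% random dropout, normal errors, correlation 0.5, 40,000 trials per cell. Monte Carlo standard error is about 0.2 points at 0.59, and 0.1 at 0.80 and for type I error.

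Power with HC2 and a t reference, baseline-only → factors added:

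| Share | at 0.59 SD | at 0.80 SD |
|---|---|---|
| 0% | 79.5 → 79.0% | 96.7 → 96.3% |
| 5% | 79.8 → 80.7% | 96.7 → 96.9% |
| 10% | 80.5 → 83.0% | 97.1 → 97.7% |
| 20% | 81.2 → 86.9% | 97.4 → 98.7% |

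Against the plan read literally (baseline-only, HC0, t reference), the whole change is worth about −2, 0, +1 and +4 points at 0.59, and −0.7, −0.1, +0.4 and +1.0 at 0.80. The break-even share at 0.59 is about 5-6%.

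Type I error:

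| Model | 0% | 5% | 10% | 20% |
|---|---|---|---|---|
| Baseline-only, HC0, normal | 6.0% | 5.5% | 5.2% | 4.2% |
| Baseline-only, HC0, t | 5.6% | 5.1% | 4.8% | 3.9% |

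With the factors added, over the four shares:
- HC0, normal reference: 6.6-6.7%
- HC0, t reference: 6.1-6.3%
- HC2, t reference: 5.0-5.2%

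**Robustness.** I varied the error distribution (lognormal, t with 5 df), the band-arm variance (2× and 3×), lognormal errors with 2× variance, factor frequencies (70/40/30% and 80/50/20%), and block size (2 and 6). One further variant made the first 22 participants all diabetic, because section 12 starts enrolment with people with diabetes. At shares 0, 10 and 20%, the like-for-like change at 0.59 stayed within −0.3 to −0.7, +2.2 to +2.7 and +4.5 to +6.0 points. With the factors in the model, type I error was 4.3-5.3% for HC2 with t and 6.0-6.9% for HC0 with a normal reference.

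**The case against.** The strongest reply is that nothing is broken. Section 9.3 powers exactly the model that 9.1 specifies, and stratification delivers balance whatever model is fitted. The protocol expects a large effect: "The differential in projected effect sizes between band-induced weight loss (~0.99) and metformin (~0.18) is ~0.80". At 0.80, power is about 97% and the proposed package moves it by −0.7 to +1.0 points against the literal plan. A gain needs demanding assumptions: a 10% share asks each factor, sex included, to shift the outcome by 0.32 SD after baseline, about the 0.33 that 9.3 gives for troglitazone vs placebo. Below a share of 5-6% the package has slightly less power than the plan at 0.59. The HC0 problem becomes noticeable only once covariates are added. Finally, section 11.9 requires investigator and DSMB approval and IRB resubmission for any amendment.

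Most of this stands, and it is why the point is only one to consider. Section 2.3 supports a small share: "we have observed a fairly linear decline" in β-cell compensation across pre- and mild T2D, so the baseline value may already carry much of the diabetes information. Three things weigh against dropping the point. The 0.80 is 3 × 0.33 minus 0.18, extrapolated from other studies, so performance near 0.59 is also relevant. More than half of the loss at share zero comes from removing HC0's liberality. And 9.1 leaves the sandwich version and reference distribution open, which is an analyst's choice in an unmasked trial whichever covariates are used.

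**Conclusion.** The point holds, as an optional refinement. The primary and secondary ANCOVA omit the factors the trial randomises by, and no section gives a reason. The planned analysis remains valid and the 9.3 power figures stand. The planned test is mildly liberal only if the factors are barely prognostic (5.6-6.0% with HC0), and it is conservative if they explain much (3.9-4.2% at a 20% share).

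Like for like, adding the factors costs about half a point of power at 0.59 SD if they explain nothing, and gains about 2.5 points at a 10% share and 5.7 at 20%. At 0.80 SD the change runs from −0.4 to +1.3 points. The size of the gain rests on the assumed shares, which the documents do not supply. The direction and the small downside were stable over the error distributions, variance ratios, factor frequencies and block sizes tried.

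**What to change.** In 9.1, and by reference in 9.2, write for example:

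> The ANCOVA will include treatment, the baseline value of the endpoint, sex, BMI at entry (<35 vs ≥35 kg/m²) and diabetes at entry (yes/no) as main effects. Diabetes status is coded for all participants, including those randomised before IDE approval. Standard errors are HC2, with a t reference on the residual degrees of freedom.

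The two parts belong together: the factors should not be added with uncorrected HC0. Three main effects are preferable to eight stratum indicators with about 70 completers.

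If the investigators prefer the baseline-only model, one sentence giving the reason, the sandwich version and the reference distribution is enough.

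Cost: one or two sentences through the amendment route in 11.9, no new data, and 3 of about 67 degrees of freedom. If the factors turn out not to be prognostic, power against baseline-only HC0 with t falls from 80.8% to 79.0% at 0.59 SD and from 97.0% to 96.3% at 0.80 SD. At 0.59, about half a point of that comes from the added factors and the rest from correcting HC0. The text should be settled before any outcome data are analysed by arm.

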adverse effects of obesity through weight loss that is more than can be sustained with lifestyle modification and which occurs without the potential confounding effect of direct stimulation of insulin secretion seen with operations that bypass the foregut. Metformin treatment will reduce insulin resistance and lower glucose levels. By comparing changes in  $\beta$ -cell function between treatment groups, we will compare the most commonly used medical monotherapy to a surgical approach for long-term effects on  $\beta$ -cell health. By examining changes in potential mediators of fat-induced  $\beta$ -cell deterioration, we may identify mechanisms for  $\beta$ -cell preservation that could serve as future therapeutic targets or markers of response to treatment. Based on data from weight loss and metformin in extant diabetes prevention trials and the greater weight loss expected with banding, we hypothesize that gastric banding will be more effective than metformin treatment at preserving or restoring  $\beta$ -cell function. We propose three specific aims to test this hypothesis and examine potential mechanisms for  $\beta$ -cell preservation or restoration.

**AIM 1 – Clinical Study:** We will conduct a prospective, randomized, 24-month study in obese individuals with pre-diabetes or mild T2D using two different approaches to mitigate the metabolic effects of obesity: (a) gastric banding and (b) metformin.

AIM 2 – Impact on  $\beta$ -cell Health: We will compare changes in markers of  $\beta$ -cell health, primarily  $\beta$ -cell compensation for insulin resistance, between groups. We predict that banding will improve  $\beta$ -cell health more than metformin will.

AIM 3 – Mechanisms Linking Fat to  $\beta$ -cell Health: We will measure body fat (total and regional by DEXA, abdominal distribution by MRI), along with potential circulating mediators of  $\beta$ -cell decline and use regression methods to identify mechanisms by which obesity may influence  $\beta$ -cell health and identify clinical markers thereof.

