## **1.3 Overall Design and Study Interventions**

BetaFat is a two arm, unblinded study in which volunteers with prediabetes or drug-naïve, recent onset, mild type 2 diabetes will be randomized to: (1) metformin or (2) gastric banding. The study will recruit patients over a 27-month period and follow each individual for a total of 24 months on study intervention. The primary outcomes will be  $\beta$ -cell compensation for insulin resistance, measured in two ways as defined below. The anticipated duration of the BetaFat study is five years, including pre-trial preparation and post-trial analysis and reporting.

ß-cell function,  $\alpha$ -cell function, insulin sensitivity and glucose tolerance will be assessed using intravenous and oral tests. Both intravenous and oral tests will be obtained at baseline and after 12 and 24 months of therapy. Use of oral and intravenous tests will allow us to examine different aspects of  $\beta$ -cell function. Such use will also allow us to examine how well relatively simple measures of  $\beta$ -cell function,  $\alpha$ -cell function and insulin sensitivity (i.e., from fasting samples and oral glucose tolerance tests) correlate to more sophisticated measures (i.e., from glucose clamp studies) in the prediction of  $\beta$ -cell decline and/or response to treatment. Finally, a series of adipokines/inflammatory markers will be measured to determine whether they predict changes in  $\beta$ - and  $\alpha$ -cell function, insulin sensitivity and glucose tolerance without and with therapy.

Clinically, the project will serve as a test of concept for use of gastric banding relatively early in the spectrum of obesity and  $\beta$ -cell disease. We will derive information on the extent of weight loss necessary to fully arrest or reverse the  $\beta$ -cell disease, as well as potential clinical markers for successful treatment. Biologically, the results will provide crucial information on potential mediators of  $\beta$ -cell failure and its arrest or reversal in the context of obesity. Those mediators will guide the development of more effective strategies for prevention and early treatment of T2D with the aim of arresting or reversing the progressive  $\beta$ -cell disease.

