# **3 STUDY DESIGN**

## 3.1 Overview and Rationale

The BetaFat study protocol described herein will involve 88 adults who are 20 – 65 years old and who have prediabetes or drug-naïve, recent onset and mild type 2 diabetes. Additional inclusion and exclusion criteria are defined below. Participants will be randomized over a 27 month period to either metformin or gastric banding in an open treatment format. The primary outcome will be rate of change in ß-cell compensation for insulin resistance, as defined below. Figure 3 provides an overview of the types and timing of main study procedures.

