# 3.2 Primary Endpoints

The primary objective of the RISE Study is to evaluate the effects of randomized treatment on ß-cell function, measured by hyperglycemic clamp techniques. Given that insulin and C-peptide are both used in quantifying ß-cell function, each of them will be measured in certain or all tests in part to avoid the problem of collinearity when performing the statistical analyses. Two co-primary endpoints are specified:

- Change between baseline and end study in ß-cell function measured as the second phase response (steady-state of the hyperglycemic clamp; 100-120 minutes of glucose infusion). This will be calculated as mean C-peptide at steady state, adjusted for insulin sensitivity (ratio of the glucose infusion rate:plasma insulin concentration at steady state).
- Change between baseline and end study in β-cell function measured as AIRmax (arginine-induced acute insulin response at hyperglycemia glucose; β-cell secretory capacity) [30]. This will be calculated as the incremental area under the C-peptide curve from 0-10 minutes following arginine injection at a plasma glucose ≥450 mg/dl, adjusted for insulin sensitivity measured by the hyperglycemic clamp.

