intensify messaging about the importance of participation and identify reasons for drop-outs, targeting them for retention efforts; (b) we may increase overall enrollment if the difference between real and projected drop-outs is small (budgets limit large increases in enrollment); (c) we will examine projected completion in relation to power, noting that our current 80% power threshold is below the projected effect size, so that we may be able to tolerate some excess loss to follow-up; (d) if dropouts are occurring after 12 months, we may consider changing the primary outcomes to rates of change in the two primary beta cell measures, as we have used in prior observational studies with different durations of follow-up. Note that we plan to assess main outcomes at 12 and 24 months on treatment, allowing this approach.

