## **11.9 Protocol Amendments**

Adoption of protocol amendments for elements that are shared between BetaFat and other studies in the RISE Consortium requires two-thirds majority approval by voting members of the RISE Steering Committee and approval by the DSMB. Amendments that involve protocol elements specific to BetaFat require only approval of the local BetaFat investigators and the DSMB. The amended protocol is resubmitted to the local IRB, and the participant consent is revised appropriately.

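### Must the plan say how a split between its two primary endpoints, each tested at 0.05, bears on its single hypothesis?

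*Combined protocol and SAP*

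**What the plan says.** Section 1.2 hypothesizes "that gastric banding will be more effective than metformin treatment at preserving or restoring" β-cell function, and offers three aims to test this and to explore mechanisms.

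Section 3.2 announces "Two co-primary endpoints are specified": the steady-state second-phase C-peptide response and the arginine-stimulated AIRmax, each adjusted for insulin sensitivity. Section 1.3 speaks of primary outcomes, in the plural, that represent β-cell "compensation for insulin resistance, measured in two ways as defined below". Section 3.1 alone uses the singular: "The primary outcome will be rate of change in" β-cell compensation.

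Section 9.1 states that the two outcomes are "analyzed separately with a total type I error probability of 0.05 for each, i.e. without an adjustment for 2 separate outcomes".

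Section 9.3 gives power for one comparison with 35 completers per group. A t-test detects 0.68 with 80% power. ANCOVA with a baseline correlation of 0.5 has 89% power at 0.68, or will "give us 80% power to detect a minimal effect size of 0.59". The projected effect is about 0.80. Section 5.4(c) says of excess dropout: "we will examine projected completion in relation to power, noting that our current 80% power threshold is below the projected effect size".

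**The concern.** One hypothesis, two tests at 0.05 and no rule for combining them can leave room for a choice after the data are seen. If a win on either endpoint were taken to support section 1.2, the chance of a false claim would exceed 5%. If both wins were needed, the power for that claim would fall below the 80% in 9.3. The trial is unmasked, and 5.4(c) uses the power to judge how much extra dropout can be borne, so the missing rule might affect conduct as well as reporting. The labels also seem to vary between one outcome, one construct measured twice, co-primary endpoints and separate outcomes.

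**Working it through.** **Inputs.** From the documents: 35 completers per group, two-sided 0.05, baseline correlation r = 0.5, and effects 0.59, 0.68 and 0.80 (section 9.3); no adjustment for two outcomes (section 9.1). Assumed, because the documents give no figure: a correlation between the two endpoint test statistics of 0, 0.5, 0.7 or 0.9.

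**1. The plan's own figures.** Power comes from the noncentral t distribution, with noncentrality d·√(n/2) for the t-test (68 df) and d·√(n/2)/√(1 − r²) for ANCOVA (67 df).

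- t-test at 0.68: 0.68 × √17.5 = 2.845; power 80.1% (stated 80%).
- ANCOVA at 0.68: 2.845/√0.75 = 3.285; power 89.9% (stated 89%).
- ANCOVA at 0.59: 0.59 × √17.5/√0.75 = 2.850; power 80.2% (stated 80%).
- ANCOVA at 0.80: 0.80 × √17.5/√0.75 = 3.864; power 96.8%.

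The stated figures reproduce as power for a single endpoint.

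**2. What other rules would give.** None of these rules is in the plan. The bivariate normal distribution is used, with equal effects on both endpoints unless noted.

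| Rule | Quantity | Correlation 0 to 0.9 |
|---|---|---|
| Each endpoint stands alone (section 9.1) | Power at 0.59; at 0.80 | 80.2%; 96.8% |
| Either suffices, unadjusted | Type I error, both directions | 9.75% to 7.0% |
| Either suffices, unadjusted | Type I error in favour of banding (one endpoint: 2.5%) | 4.9% to 3.5% |
| Both required | Power at 0.59 | 64% to 75% |
| Both required | Power at 0.80 | 94% to 96% |

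With independent endpoints these are simple products: 1 − 0.95² = 0.0975 for the error, and 0.802² = 0.643 and 0.968² = 0.937 for joint power.

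**3. How often a split would occur.** The chance of exactly one significant result is p₁ + p₂ − 2·P(both).

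- 0.80 on both endpoints: 6% to 3%. At correlation 0: 2 × 0.9677 − 2 × 0.9365 = 0.062.
- 0.59 on both endpoints: 32% to 10%.
- 0.80 on one and 0.40 on the other: 49% to 52%. The 0.40 is an assumption with no source in the documents.

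**4. Headroom in section 5.4(c).** Completers per group needed for 80% power at 0.80:

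| Basis | One endpoint | Both required | Margin below 35 |
|---|---|---|---|
| ANCOVA, r = 0.5 | 20 | 26 to 22 | 15; 9 to 13 |
| t-test | 26 | 34 to 29 | 9; 1 to 6 |

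Some margin remains in every cell. It is thinnest, at one per group, for the unadjusted t-test with both endpoints required and no correlation between them. The planned primary analysis is ANCOVA.

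**5. The labels side by side.** Sections 1.3, 3.2, 5.4(d) and 9.1 all refer to two primary outcomes or measures. Only 3.1 is singular, and it defers to the definitions that follow.

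**The case for a change.** The best argument for a change is that testing separately fixes the tests but not how they bear on the one hypothesis in 1.2. Sections 1.2, 3.2, 9.1, 9.3 and 9.4 are silent on a split. Section 9.3 projects one effect for β-cell compensation and none per endpoint, so equal effects cannot be presumed, and with unequal effects a split could be common. A sentence written now would cost no patients and no alpha.

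The silence is real, and so is the possibility of a split. Less follows than it seems. The hypothesis in 1.2 is a scientific expectation, and Aim 2 addresses it by comparing several markers of β-cell health. Section 9.4 calls the trial a proof-of-principle study, and no decision in the documents turns on a single pass or fail verdict. Both results will be on view with the lack of adjustment disclosed, so a reader can apply either stricter rule.

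Nor is the obvious added sentence neutral. To say that one significant endpoint does not by itself establish the hypothesis leaves open what would. If the answer is both endpoints, that brings in a joint rule the plan did not adopt, and per-endpoint power would no longer be the relevant figure. A Holm procedure is a trade-off, not a correction: where only one endpoint responds, at 0.59, its power falls from 80% to 71%. Any wording would also need DSMB approval and IRB resubmission under section 11.9. If the element is shared across the consortium, it "requires two-thirds majority approval by voting members of the RISE Steering Committee and approval by the DSMB".

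**Conclusion.** No change follows. The choice of 0.05 for each endpoint is disclosed and coherent: each result carries its own conclusion, and the error rate and power in 9.1 and 9.3 are correct on that basis. The only departures come from rules the plan does not propose. Even the stricter one keeps power at about 94% or more at the projected 0.80 with 35 completers, given ANCOVA with r = 0.5 and equal effects on both endpoints. At 0.59 it would give 64% to 75%, but the plan never claims joint power. Section 5.4(c) sets no dropout number and says only that some extra loss might be tolerable, which remains true under each power rule examined.

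What remains is a gap in detail that analysts can fill sensibly: report a split as one endpoint significant and one not, without a single overall claim. There is also one clerical slip, the singular outcome in 3.1. Stating either point would alter no test, alpha, sample size or result. The conclusion rests on reading 9.1 as written. A later claim that a win on either endpoint alone confirms the hypothesis would carry a two-sided error of about 7% to 10%, and should be judged on that footing.
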